10.3 Adverse Event Reporting – Procedures for Investigators

The Principal Investigator and co-investigators will review any AEs and report any SAEs to the Sponsor as soon as possible and within 24 hours of obtaining knowledge of the event. The Principal Investigator and co-investigators will promptly report AEs to the Partner's Institutional Review Board (IRB) and to the BU IRB (unless oversight is ceded by the BU IRB to the Partners IRB), in accordance with local requirements.

[name] is the Sponsor of the Investigational Device Exception for the BP and Zealand Pharma A/S is the Sponsor of the IND for ZP4207.

Reports of AEs will be submitted to the FDA in compliance with the terms of the Code of Federal Regulations.

All events meeting the definition of an AE must be collected and reported from the first trial-related activity from Visit 3 until the end of the post-treatment follow-up period. At each contact with the site (visit or telephone, excluding safety visits, where the patient is not seeing the Investigator or staff [e.g., visits to the laboratory], the patient must be asked about AEs. All AEs, either observed by the Investigator or reported by the patient, must be recorded by the Investigator and evaluated.

The Investigator should record the diagnosis, if possible. If no diagnosis can be made, the Investigator should record each sign and symptom as individual AEs. All AEs must be recorded by the Investigator. One single AE Form must be used per AE from start to resolution. For SAEs, the SAE Form must also be completed.

AE information should include the following:

- Patient identification number on all pages
- Date and time of treatment start
- Date and time of onset and date of outcome
- Date and time of Investigator's first information on the (S)AE
- Seriousness
- Severity
- Causal relationship with IMP ZP4207
- Causal relationship with IMP insulin
- Causal relationship with IMP glucagon
- Causal relationship with medical device
- Causal relationship with procedures
- Interruption or withdrawal of treatment with IMP or medical device and other measures taken
- Outcome

Clinical Trial Protocol
ZP4207-16051

Version number: 8.0
Amendment 7.0
Date: 06 January 2017

All AEs are coded; details are described in the trial specific Data Management Plan.

The Investigator must report initial information in writing on the SAE Form for all SAEs to the Sponsor's responsible pharmacovigilance unit (here: Lindeq) immediately (within 24 hours) after obtaining knowledge about the event.

Name: [REDACTED]
Company: Lindeq
Address: [name]
Tel: [REDACTED]
Fax: [REDACTED]
Mobile: [REDACTED]
E-mail: [contact]

In addition and meeting the same timeline, Investigators must report all SAEs to Zealand Pharma A/S by forwarding the SAE Form electronically within 24 hours of obtaining knowledge of the event to the representatives of Zealand Pharma A/S.

Names: [REDACTED] and [REDACTED]
Address: [name]
Tel: [REDACTED]
E-mails: [REDACTED]

It is the responsibility of Lindeq to report all SUSARs that occur in this trial to the Competent Authorities and to the Investigators. It is the responsibility of the Investigators to report the SUSARs to the IRBs in accordance with the local requirements in force and the International Conference on Harmonisation (ICH) guideline for Good Clinical Practice (GCP). The trial monitor must be informed accordingly.

It is the responsibility of Lindeq to report all serious adverse reactions on insulin lispro and glucagon for injection to the Eli Lilly Pharmacovigilance department within 5 days.

It is the responsibility of the Investigators to report all UADEs to Beta Bionics within 24 hours of the time they are detected. It is the responsibility of the Investigators to report all UADEs to the IRB in accordance with the local requirements in force and the ICH GCP. It is the responsibility of Beta Bionics to report all UADEs to the Competent Authorities.

All device deficiencies should be documented and should be reported to Beta Bionics within 24 hours. Device deficiencies are inadequacies of a medical device with respect to its identity, quality, durability, reliability, safety, or performance.

Name: [REDACTED]
Company: Beta Bionics, Inc.
Address: [name]
[name], United States
Tel: [REDACTED]
E-mail: [REDACTED]

Clinical Trial Protocol
ZP4207-16051

Version number: 8.0
Amendment 7.0
Date: 06 January 2017

10.4 Pregnancy Reporting

Female patients must be instructed to notify the Investigator immediately if they become pregnant or if they suspect to be pregnant during the trial. The Sponsor has a responsibility to monitor the outcome of all pregnancies reported during the clinical trial.

Male patients must be instructed to notify the Investigator immediately if their partner becomes pregnant or suspects to be pregnant. The Sponsor has a responsibility to monitor the outcome of all pregnancies reported during the clinical trial. During an information meeting at the trial site, the patient's partner will be fully informed by a physician of her participation in capturing the outcome data, and will be asked to provide her written consent.

The Investigator must report all information on pregnancies, including AEs in the patient/patient's partner, the fetus, and newborn infant/ toddler. The pregnancy report must be forwarded to the Sponsor preferably electronically as PDF or by fax.

The Investigator must follow the pregnancy until the pregnancy outcome and the newborn infant(s) until the age of 1 month. The Investigator must collect information on the pregnancy and pregnancy complications as well as the pregnancy outcome including the health of the newborn infant(s) on the pregnancy forms.

The following must be collected:

- Initial information of the pregnancy
- Information on the outcome of the pregnancy, including the health status of the newborn infant(s) at the age of 1 month
- All AEs in connection with the pregnancy and pregnancy outcome must be reported on the pregnancy forms. It must be clear in the description if the event occurs in the patient/patient's partner, the fetus, or the newborn infant.
- All SAEs in connection with the pregnancy and pregnancy outcome must be reported on the pregnancy forms following the same timelines as required for other SAEs. It must be clear in the description if the event occurs in the patient/patient's partner, the fetus, or the newborn infant.

The SAEs that must be reported include abnormal outcome – such as congenital anomalies, fetal death, and termination of pregnancy (spontaneous or elective abortion), including any anomalies of the fetus observed at gross examination or during autopsy – as well as other pregnancy complications (ectopic pregnancy) fulfilling the criteria of an SAE.

10.5 Hypoglycemia

Hypoglycemia will be regarded as an AE and will be recorded and documented on an AE Form. For the purposes of AE reporting, the following definitions of hypoglycemia will be used:

- Symptomatic hypoglycemia: an event during which typical symptoms of hypoglycemia are accompanied by a BG concentration ≤ 70 mg/dL
- Asymptomatic hypoglycemia: an event not accompanied by typical symptoms of hypoglycemia but with a BG concentration ≤ 50 mg/dL
- Severe hypoglycemia: an event requiring assistance of another person to actively administer carbohydrates, glucagon, or take other corrective actions

Clinical Trial Protocol
ZP4207-16051

Version number: 8.0
Amendment 7.0
Date: 06 January 2017

10.6 Safety Monitoring

10.6.1 Data and Safety Monitoring Board

An external DSMB will oversee the conduct of the trial, as set forth in the DSMB Charter. Additionally, the DSMB will be informed in the event of any serious and unexpected AEs. The DSMB will be informed if there are any changes to the trial protocol that could significantly impact the safety or scientific validity of the trial. A final DSMB meeting will convene after the completion of the trial.

The participation of individual patients will be discontinued if they experience:

- Seizure or unconsciousness associated with hypoglycemia and associated with participation in the trial
- Persistent nausea and vomiting thought to be related to glucagon dosing associated with participation in the trial
- Hospitalization associated with participation in the trial
- Pregnancy
- Diabetic ketoacidosis

If more than 1 patient must be withdrawn from the trial for these reasons, the trial will stop and a vote of the DSMB will be required to restart it. All AEs that are serious and unexpected but related will be reported to the DSMB within 5 working days.

Note that patients may discontinue participation at any time. Patients may be removed from the trial for other reasons, for instance, failure to comply with trial procedures or intercurrent illness that is unrelated to the BP but that precludes safe participation. Discontinuation of participation for these reasons will not contribute to a decision to discontinue the trial.

10.6.2 Zealand Pharma Safety Committee

The internal Zealand Pharma Safety Committee is constituted to perform ongoing safety surveillance of clinical trials within ZP4207, including this trial.

If safety signals are observed either based on reported SAEs, periodic review of laboratory parameters, planned review of all AEs reported between the safety committee meetings, or on notification of significant findings, the Safety Committee will take appropriate measures to safeguard the patients.

11 STATISTICS

For all analysis, the 2 treatment arms from Part 1 (iPhone-based BP) will be compared, and the 2 treatment arms from Part 2 (iLet) will be compared. The analysis of Part 1 will be completely separate from the analysis of Part 2.

11.1 Analysis Populations

The following analysis sets are defined in accordance with the ICH-E9 guidance:

The Full Analysis Set is based on the intention-to-treat principle and includes all randomized patients. In exceptional cases, patients from the Full Analysis Set may be excluded (will be

Clinical Trial Protocol
ZP4207-16051

Version number: 8.0
Amendment 7.0
Date: 06 January 2017

decided in the database review [DBR] meeting). In such cases, the exclusion will be justified and documented. Patients will contribute to the evaluation “as randomized.”

The Per-Protocol Set includes all patients of the Full Analysis Set who completed the trial without any major protocol violations. Patients in the Per-Protocol Set will contribute to the evaluation “as treated.” This analysis will only be used if it is different than the Full Analysis Set.

The Safety Analysis Set includes all patients receiving at least 1 dose of the IMP. Patients in the Safety Analysis Set will contribute to the evaluation “as treated.”

Analyses of efficacy endpoints will be based on the Full Analysis Set (and the Per-Protocol Set if necessary). This decision will be made in the DBR meeting. The analysis of the safety endpoints will be based on the Safety Analysis Set.

Before data are released for statistical analysis, a blinded review of all data will take place to identify protocol deviations that may potentially affect the results. At this time, it will be determined if patients and/or data should be excluded from the analysis. Furthermore, outliers will be identified by data review according to ICH-E9.

Obviously erroneous data points may be excluded from the analyses or re-analyzed (e.g., serum concentrations). The decision to re-analyze or exclude data points from the statistical analysis is the joint responsibility of the Sponsor, the Principal Investigator, and the Trial Statistician.

The patients or observations to be excluded and the reason for their exclusion will be documented and signed by those responsible prior to database release. The documentation will be stored together with the remaining trial documentation. The patients and observations excluded from analysis sets, and the reason for this, will be described in the clinical trial report.

11.2 Statistical Methods

Medpace will be responsible for the statistical analysis. The statistical planning and conduct of analyses of the data from this trial will follow the principles defined in relevant ICH guidelines and Medpace’s biostatistical SOPs. A general description of the statistical methods to be used is given in this section, specific details will be provided in the Statistical Analysis Plan (SAP), which will be prepared before database lock. All statistical analyses will be performed using SAS® (SAS Institute Inc., Cary, North Carolina, USA), version 9.3 or later.

11.2.1 Analysis of Safety

The following variables will be evaluated according to treatment for safety purposes:

Adverse Events

All AEs will be coded using the latest version of Medical Dictionary for Regulatory Activities (MedDRA). Individual AEs will be presented in a listing including relationship to trial product/device, severity, and treatment period at onset. If more than 20 treatment-emergent AEs (AEs with onset after [first] dosing at Visit 3 until the Follow-up Visit 6) are registered, a summary table including number of AEs, number of patients with at least 1 AE, and percentage

Clinical Trial Protocol
ZP4207-16051

Version number: 8.0
Amendment 7.0
Date: 06 January 2017

of exposed patients with at least 1 AE will be made by system organ class and treatment period at onset.

Local Tolerability

Local tolerability at the injection site will be summarized using descriptive statistics as appropriate.

Laboratory Safety Assessments

Laboratory assessments will be summarized. A listing of abnormal values will be provided.

Physical Examination

A frequency table will show the number and percentage of physical examination results.

Vital Signs

Vital signs will be summarized using descriptive statistics.

12-lead ECG

The Investigator's evaluations of 12-lead ECGs will be summarized and abnormal individual evaluations will be listed together with the Investigator's comments. Changes in 12-lead ECG between measurements will be recorded as AEs if the Investigator judges them to be clinically significant.

11.2.2 Analysis of Efficacy

The analysis of BP function endpoints and glycemic endpoints will be on an intention-to-treat basis. In cases where a treatment arm was not completed (and that arm was not repeated according to protocol criteria), available data from that arm will be used in the data analysis.

The Shapiro-Wilk test will be used to determine the normality of the residuals for each comparison. Summary tables that display descriptive statistics, including percentages, means or medians, and standard deviation and/or ranges, as appropriate, will be provided.

A paired t-test or the Wilcoxon signed rank test for comparison of means with normally or non-normally distributed residuals, respectively, will be used. In a secondary analysis, any period effect and any interaction between treatment and period will be looked for, although no such interaction is predicted for the efficacy outcome. Further details will be included in the SAP.

The number of patients and proportions of severe hypoglycemic events, symptomatic hypoglycemia, and carbohydrate interventions due to hypoglycemia with the event counts will be summarized descriptively, and the proportions will be analyzed by a Fisher's exact test if data allow.

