2.2 Secondary Objectives

The secondary objectives are to measure glycemic regulation, including hypoglycemia exposure (percent of time spent with CGM glucose < 60 mg/dL), evaluate BP device reliability, and to document the satisfaction of patients with the BP with the goal of optimizing the functionality and user interface of the BP.

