- Patients will exercise on a stationary bike with a heart rate from 120-140 beats per minute for a total of 4,000 heart beats (approximately 30 minutes). Patients will rate their exercise intensity using the Borg scale every 5 minutes, with the target intensity level between 12 and 14. Heart rate will be measured every 5 minutes.
- Chemistry and hematology samples will be collected immediately after end of exercise (see [Appendix B](#)).
- BG measurements will be obtained off of the IV line every 10 minutes. If BG is <80 mg/dL, BG measurements will be obtained off of the IV line every 5 minutes.
 - If BG is <50 mg/dL, the exercise will be terminated regardless of heart beats achieved.
 - Carbohydrates will be given for any BG <50 mg/dL according to the following protocol: Dextrose (g) = BSA (m²)/[1.7 m² (women) or 1.9 m² (men)] *15 g.
 - Repeat treatments will be given at 15-minute intervals as long as BG remains <50 mg/dL.

Clinical Trial Protocol
ZP4207-16051

Version number: 8.0
Amendment 7.0
Date: 06 January 2017

- If there is an interruption in the Dexcom CGM output, trial staff will assist the patient in recovering CGM data streaming. If this requires replacement of the CGM sensor, BGs will be checked every 10 minutes (every 5 minutes if BG is <80 mg/dL) using blood from the IV until the CGM is able to be calibrated again. These BGs will be entered into the BP, which will treat them as CGM values and dose insulin and/or glucagon appropriately.
- If there is a complete failure of the BP operation, patients will take over their own BG control using their personal insulin pump until the BP can be brought back online. If BP control cannot be promptly resumed (e.g., within 30 minutes), the patient may be asked to repeat that trial day once.
- Patients may choose to withdraw from the trial at any time. If they withdraw from the trial, they should alert a provider immediately.
- Just prior to the end of the study visit, vital signs including body temperature and blood pressure will be obtained and a 12-lead ECG will be performed. Orthostatic vital signs (heart rate and blood pressure) will be measured in the seated position and within 3 minutes of standing. If patients have hypotension or orthostatic hypotension, discharge will be delayed until their blood pressure is normal and stable.

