7.4.4 Response to Hyperglycemia

- Trial staff will check the infusion site, BP, and insulin pump for normal operation any time BG is >300 mg/dL. If there is any suspicion of infusion set malfunction, the site should be replaced. Trial staff will check the BP for any malfunction and correct any problems that are found. If the BG remains >300 mg/dL for 2 hours despite troubleshooting, blood ketones will be measured. If the blood ketone result is >1.5 mmol/L, the visit will be stopped and rescheduled. The patient will be provided with insulin and a syringe to give an injection based on their correction factor.
- If a patient experiences diabetic ketoacidosis, his or her participation in the trial will be discontinued.
- If no correctable fault is found, but there is doubt regarding the correct function of the BP system, the treatment visit may be stopped and the visit rescheduled.

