11.2.4 Sample Size Determination

No formal sample size calculations were made. It is expected that between 20 and 24 patients will be randomized in the trial. The sample size is based on a clinical rather than statistical

Clinical Trial Protocol
ZP4207-16051

Version number: 8.0
Amendment 7.0
Date: 06 January 2017

rationale. The sample size is considered adequate to address the primary trial objective of exploring the safety of ZP4207 when used in the BP and with reference to Lilly glucagon used in the BP.

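### Section 11.2.2 calls the analysis intention-to-treat but by implication drops the failed first attempt of a repeated treatment day, which can inflate the device-function percentages

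*Protocol*

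**What the plan says.** Section 11.2.2 opens with the principle: "The analysis of BP function endpoints and glycemic endpoints will be on an intention-to-treat basis". The next sentence, which also stands in the synopsis under the evaluation of trial data, limits it. Data from an incomplete arm are used on a condition, namely in cases "where a treatment arm was not completed (and that arm was not repeated according to protocol criteria), available data from that arm" being what enters the analysis. Nothing in the protocol says how the first attempt of a repeated arm is analyzed.

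A started day can be replaced in three ways:

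- Complete BP failure (section 7.4.1): "If BP control cannot be promptly resumed (e.g., within 30 minutes), the patient may be asked to repeat that trial day once".
- Doubt about BP function with no correctable fault found, in the hyperglycemia section only (7.4.4): "the treatment visit may be stopped and the visit rescheduled".
- Glucose above 300 mg/dL for 2 hours despite troubleshooting, followed by a ketone test (7.4.4): "If the blood ketone result is >1.5 mmol/L, the visit will be stopped and rescheduled".

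Section 2.2 makes it a secondary objective to "evaluate BP device reliability". Section 8.2.1 measures this by the percent of 5-minute steps functioning and the percent of dose amounts issued and delivered. Section 8.2.2 includes CGM time above 300 mg/dL.

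**The concern.** Under an intention-to-treat label one expects every started treatment day to count. Here an incomplete day counts unless it was repeated, and the reasons for repeating are poor values, or close correlates, of what is being measured. A day on which the device failed outright contributes its low percentage if nobody repeats it. If it is repeated, it is represented by the second try.

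Replacement therefore depends on the outcome, and for the BP-function percentages it works in one direction: upward. Two of the three routes are also discretionary, in an open-label trial. At stake is a stated secondary objective, in a feasibility trial whose data are meant to guide the next device generation. Failures are foreseeable, since section 1.1 describes recurrent lost connections among the components of the iPhone-based system.

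**Working it through.** There is no planned figure to reproduce. Section 11.2.4 states: "No formal sample size calculations were made". The protocol gives neither a failure rate nor an expected percent of functioning steps.

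**Step 1: does the text drop the failed attempt?** Two cases are possible for an incomplete arm.

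| Case | What 11.2.2 says |
|---|---|
| Incomplete, not repeated | available data used |
| Incomplete, repeated | silent; excluded from the sentence by the parenthesis |

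If the first attempt were used in both cases, the parenthesis would do nothing. Exclusion is thus implied, though not written out.

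**Step 2: do the triggers overlap the endpoints?**

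| Trigger | Overlapping endpoint |
|---|---|
| Complete BP failure, not promptly resumed | percent of steps functioning; percent of doses issued and delivered |
| Doubtful BP function (hyperglycemia section) | the same, plus time above 300 mg/dL |
| Glucose above 300 mg/dL for 2 hours with ketones | time above 250 and 300 mg/dL; mean CGM glucose |

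**Step 3: illustrative size for the percent of functioning steps.**

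- Inputs from the protocol: a visit of about 8 hours (7.4.1), 5-minute steps (8.2.1), up to 10 patients per part with two days each (3.1).
- Steps per day: 8 × 60 / 5 = 96. The 30-minute example in 7.4.1 is 6 / 96 = 6.25% of a day.
- Assumptions: working days function on g = 98% of steps; a failed day functions on f = 0% to 75% of the planned 96 steps (failure between Hour 0 and about Hour 6), with all later steps counted as non-functioning; the repeat is a normal working day.
- Arm mean with k failed days kept: [(10 − k) × g + k × f] / 10.

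| k | g | f = 0% | f = 75% | failed days replaced |
|---|---|---|---|---|
| 1 | 98% | (882 + 0) / 10 = 88.2% | (882 + 75) / 10 = 95.7% | 98.0% |
| 2 | 98% | (784 + 0) / 10 = 78.4% | (784 + 150) / 10 = 93.4% | 98.0% |
| 1 | 95% | (855 + 0) / 10 = 85.5% | (855 + 75) / 10 = 93.0% | 95.0% |

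At g = 98%, one replaced day adds 98.0 − 95.7 = 2.3 to 98.0 − 88.2 = 9.8 points.

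**Step 4: how much rests on counting to Hour 8?** Suppose the failure comes at Hour 2 and only data up to the failure are used. That day then reads 98% and nothing changes. If data run to a stop 30 minutes after the failure, the day reads 24 × 0.98 / 30 = 78.4% and the arm mean is (882 + 78.4) / 10 = 96.0%, so replacement adds 2 points.

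**Step 5: is a failed day likely?** Assume a per-day failure probability of 5%, 10% or 20%, with days independent. The chance of at least one failed day among the 20 days of a part, 1 − (1 − p)^20, is then 64%, 88% or 99%.

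No figure is given for the glycemic endpoints. The trigger is a blood glucose value and the endpoint is CGM time, and the repeat day's own values are unknown.

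**The case against.** The strongest reply has four parts.

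1. *The exclusion is only inferred, and the details are left to the SAP.* It is an inference, and section 7.4.4 speaks of rescheduling where 11.2.2 speaks of repeating, so even the match of terms is not explicit. But the protocol has already fixed a rule whose plain sense runs against its own label. An SAP that follows it would carry the problem forward.

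2. *Failures remain visible.* Section 7.4.2 collects time off BP control, section 8.2.1 lists technical faults, and section 10.3 requires all device deficiencies to be documented. None is restricted to analyzed days. This stands. What is distorted is the set of summarized percentages and CGM metrics, not the record of faults.

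3. *The size depends on assumptions.* This also stands, as Step 4 shows. It is a further reason to fix the denominator in advance.

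4. *For ZP4207 against glucagon, a complete repeat may be the better day.* A first attempt cut short before lunch (Hour 3 to 4) and exercise (Hour 6 to 7) is hard to pair with a full day, and after complete BP failure patients control glucose with their own pump. This stands, so the first attempt need not be primary for the glycemic comparison.

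A reader might go further and infer that the results come only from days that worked. The documents do not support that. Repeats after BP failure are optional and limited to one, unrepeated incomplete days are kept, CGM interruptions are managed within the day, and under 7.4.3 a doubtful system may be exchanged for a backup. A reader might also infer that the treatment comparison is biased. That is possible under discretionary repeats, but nothing shows repeats would differ by treatment, and both arms of a part use the same platform and algorithm.

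**Conclusion.** The point holds for the BP-function percentages. As written, section 11.2.2 and the synopsis contradict their intention-to-treat label by letting the failed attempt of a repeated day drop out, and the triggers for repeating overlap the outcomes. Some of the worst days, not all of them, can leave the analysis.

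One replaced day in an arm of 10 inflates mean device function by about 2 to 10 points if working days run at 98% and steps after a failure count as non-functioning. The distortion is smaller, or absent, if only steps before the stop or failure are counted. The actual size cannot be derived because no failure rate is given. For the glycemic endpoints, the defect is that the protocol does not openly say which attempt counts.

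The primary endpoint is safety and tolerability, and the sentence at issue does not govern it. This is a should-fix.

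**What to change.** Amend the sentence in section 11.2.2 and its copy in the synopsis together:

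- BP-function endpoints include every started treatment day, including days later repeated or rescheduled. Steps from an unresolved failure to the planned end of the visit (about Hour 8) count as non-functioning.
- The number of repeated or rescheduled days is reported by treatment and platform.
- For glycemic endpoints, the primary attempt is named before database lock. A complete repeat is defensible. A sensitivity analysis uses the available data from the first attempt.

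The clinical rules for repeating, rescheduling and stopping a visit stay as they are. The cost is a change of analysis wording and one extra table. The downside for the sponsor is that the reliability percentages will look less favorable if any day fails.
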